### **3.3.2 Subject Completion**

The subject has completed the study after completion of the Exit Visit procedures at the 3-Week Follow-Up Visit. Subjects who require further follow-up for an adverse event (AE) will be followed according to [Section 5.1.8](#).

### **3.3.3 Subject Discontinuation**

A subject MAY be discontinued (at the discretion of the Investigator, the Sponsor, and/or the IRB) prior to the final study visit for a variety of reasons, including, but not limited to:

- An AE occurring during the course of the study, which precludes continued treatment or follow-up

- Persistent Grade 3 or 4 slit lamp findings
- Persistent study-related symptoms/complaints
- Unacceptable contact lens visual acuity (VA)
- Unacceptable contact lens centration
- Unacceptable contact lens movement
- Failure to follow study procedures

A subject MUST be discontinued prior to the final study visit for any of the following reasons:

- Voluntary withdrawal
- Death
- Investigator decision that it is not in the best medical interest of the subject to continue participation in the investigation
- Lost to follow-up ([Section 3.3.4](#))
- Either eye is discontinued
- Becomes pregnant during the study

Prior to discontinuing a subject, every effort should be made to contact the subject, schedule a final study visit, obtain as much follow-up data as possible, and retrieve all study materials. Adverse events will be followed as described in [Section 6.0](#).

Subject discontinuations must be documented clearly on the source document and applicable eCRF. The Investigator should indicate the PRIMARY (one) reason that the subject was discontinued for each eye. Subjects who voluntarily withdraw from the study are not required to provide a reason for their decision but should be encouraged to share this information. Subjects who are discontinued from the study following enrollment will not be replaced.

Exit Visit assessments should be completed for early discontinued subjects, if possible.

At the final study visit, all study subjects who are discontinuing should be examined to ensure that their ocular health is consistent with pre-study, baseline conditions. Any adverse effects determined to have been reasonably caused by participation in the study will be followed per the standard of care. Participation in the study will not impact post-study choices of study subjects for correcting their vision using marketed products (e.g., contact lenses and contact lens care solutions).

Whether a subject completes or is discontinued from the study, they will be directed by the Investigator to resume their habitual method of vision correction.

### **3.3.4 Lost to Follow-up**

Subjects who did not return for scheduled follow-up visits, as defined by the visit window, and could not be contacted via 2 telephone calls and 1 letter with delivery confirmation, are to be considered lost to follow-up. All attempts to contact the subject should be documented and kept with the subject's source documentation, and the applicable eCRFs will be completed. If the Investigator determines that a subject has been lost to follow-up, the "study exit date" should be recorded as the last successful contact or the date a certified

letter was sent. Just prior to database lock, the database will be reviewed for all lost to follow-up entries to confirm, once again, that contact with the subject was never made. A study subject may withdraw from the study at any time for any reason.

### **3.4 Investigators**

The study will be conducted at approximately 20 investigative site(s) located in the US by Investigators who are determined by Bausch + Lomb to be suitably qualified by training and experience to conduct this study. This will include appropriate current state licensing and study-specific training. Principal Investigators will sign the Device Investigator Agreement Form prior to the start of the study. Investigators will be compensated for their services with appropriate standard professional rates. Compensation will not be dependent on the study outcomes.

Each Investigator will enroll approximately 15 subjects (30 eyes). In the event that selected sites do not meet full enrollment, the Sponsor may decide to increase enrollment as needed at other currently active sites and/or additional site(s) may be added to satisfy the enrollment requirements of the.

### **3.5 Finances**

The study will be financed through Bausch & Lomb Corporate Research & Development. A Clinical Trial Agreement will be executed between Bausch + Lomb and each Investigator prior to their participation in the clinical trial. The agreement will include the responsibilities of each party, payment and reimbursement procedures and requirements, intellectual property and publication terms, insurance and indemnification, coverage for subject injury. Investigator and subject compensation are outlined in the Investigator's Clinical Trial Agreement.

### **3.6 Study Duration**

Investigators will have 4 weeks from the enrollment start date communicated by the Sponsor to conduct the Screening/Dispensing Visit.

Subjects will be followed for approximately 3 weeks (unless discontinued or lost to follow-up) from the initial Screening/Dispensing Visit and must adhere to the following schedule:

SCHEDULED FOLLOW-UP VISITS		
Visit	Target	Acceptable Visit Range
V1: Screening/Dispensing Visit	Day 1	Not applicable
V2: 1-Week Follow-Up Visit	Day 8	Day 6-10 (5-9 days after V1)
V3: 3-Week Follow-Up Visit	Day 23	Day 20-26 (19-25 days after V1)

A visit scheduling table will be provided in the initial study shipment to aid the Investigator in scheduling follow-up visits.

## **4.0 STUDY MATERIALS**

Bausch + Lomb will provide all study materials at no charge to the Investigator. Sites will be provided with fit sets and dispensing sets for the Bausch + Lomb (kalifilcon A) Daily

Disposable Multifocal Contact Lenses and dispensing sets for the Bausch + Lomb INFUSE® Contact Lenses. All other materials will be provided to the site prior to the start of the study. Refer to [Section 4.6](#) for ordering replacement test lenses in the case of loss or damage.

Subjects will be provided with lens cases in which to dry stack their used lenses. All used and unused lenses will be returned to the Sponsor at end of the study.

Subjects must use only study-supplied lenses. Use of other contact lenses is not allowed and will be considered a protocol deviation.

#### **4.1 Description of Investigational Test Article (Test)**

The Test lens to be used in this study is the Bausch + Lomb (kalifilcon A) Daily Disposable Multifocal Contact Lens, manufactured by Bausch & Lomb Incorporated, Rochester, NY. The description of the Test lens is as follows:

- Sphere power: -6.00 D to +3.00 in steps of 0.25 D
- Add: High and Low
- Diameter: 14.2 mm
- Base curve: 8.6 mm
- Material: kalifilcon A
- Packaging solution: phosphate-buffered saline solution

The investigational test article(s) for this study are manufactured and verified under a controlled process according to the applicable regulations. With regard to those aspects, every precaution has been taken to protect the health and safety of study participants. per B&L SOP TD-GEN-FRM-039 Clinical Scorecard Evaluation

#### **4.2 Description of Control Product (Comparator)**

Not applicable; this is a single-treatment study evaluating the product performance of a new silicone hydrogel multifocal daily disposable contact lens.

#### **4.3 Instructions for Use and Administration**

Each enrolled subject will be assigned a subject number. Each eligible subject will be issued a supply of study contact lenses and will wear these lenses on a daily disposable wear basis for the duration of the study. The Investigator or designee will instruct all subjects to adhere to the Subject Instructions provided ([Appendix C](#)).

Note: Subjects may continue to use their habitual rewetting drops as needed.

##### **4.3.1 Storage Requirements**

All study lenses provided by the Sponsor must be stored in a secure location accessible only to study personnel and maintained at ambient room temperature.

##### **4.3.2 Subject Instructions**

- a) All must be given Subject Instructions for the use of the study lenses ([Appendix C](#)). Subjects must comply with the instructions provided to them. Subject Instructions will be supplied to the Investigator by Bausch & Lomb (or CRO) for distribution to the subject.

- b) The Investigator or other designee must review, with the subject, the Subject Instructions and the precautions and warnings, as appropriate for the study.
- c) Any subject who does not follow instructions to a degree that, in the Sponsor's or Investigator's opinion, jeopardizes the subject's well-being or the validity of the study should be discontinued.

#### 4.3.3 Fitting Guide

The Investigator will be supplied with a Fitting Guide for fitting the study lenses ([Appendix D](#)).

#### 4.4 Packaging and Labeling

The study lenses will be provided by Bausch + Lomb and will be packaged in a blister pack with an investigational label. The label will contain the following information at minimum:

- Lens power
- Base curve
- Diameter
- ADD power
- Lot number
- Expiration date
- Manufacturer's name
- Manufacturer's place of business
- Caution statement

#### 4.5 Other Materials

All subjects will be dispensed lens cases for return of dry-stacked worn study lenses to the Investigator during the study. Subjects that habitually use rewetting drops may continue to use their drops. ***OTHER CONTACT LENS CARE PRODUCTS ARE NOT ALLOWED TO BE USED.***

Investigators will return all worn and unworn study lenses to the Sponsor at the end of the study.

#### 4.6 Product Replacement

Subjects will be given an adequate supply of study lenses to wear on a daily disposable basis for the duration of the study.

Should the site's inventory be low or depleted, additional inventory of lenses can and must be ordered from Bausch & Lomb Clinical Supply Chain by sending a Stock Material Order Form for Study 916 to email: [REDACTED]

#### 4.7 Accountability and Traceability

Designated site staff will be responsible to keep current and accurate records of study materials during the study. The records will include receipt and acknowledgement of all study lenses. The disposition of study lenses dispensed and returned by the subjects will be recorded on study product accountability logs. The study lenses are to be dispensed only to subjects enrolled in the study, in accordance with the conditions specified in this protocol.

Upon completion of the study, a Clinical Monitor will review and verify the Investigator's accountability logs.

Following verification, and as directed by the Sponsor, all used and unused study supplies (study lenses) must be returned to the Sponsor at the address below:

#### 4.8 Masking/Unmasking

This is an open-label study.

#### 4.9 Product Risk Assessment

Information concerning potential risks associated with the investigational device (as well as possible interactions with concomitant medical treatments and risk-to-benefit ratio) can be found within the Investigator's Brochure. Risks are also summarized within the Informed Consent document. The assessments required for the study are routinely performed and are standard of care for contact lens wearers. The subjects will be informed of any potential study specific risks in the ICF or if new risks become apparent during the study.

### 5.0 STUDY METHODS

#### 5.1 Study Visits

Refer to [Appendix A](#) for a schedule of visits and parameters and [Appendix B](#) for methods of clinical evaluation.

Following identification of a potential subject, the Investigator (or designee) will explain the purpose of the study, procedures, risks/benefits, and subject responsibilities to the potential subject. The subject's willingness and ability to meet the follow-up requirements of the study will be determined. If the subject chooses to participate in the investigation, written informed consent will be obtained. The subject and the person obtaining written consent will sign and date the IRB-approved ICF. Both the Investigator and subject must keep the signed ICF document. The Investigator should retain the signed original document in the subject's record and provide a copy to the subject. In addition, the applicable privacy regulation requirements must be met.

Eligible subjects will be required to complete and initial the subject-completed forms while at the visits listed below. The data will then be transcribed into eCRFs by qualified site personnel. The original subject-completed forms will be retained by the site in the study files.

Visit Name	Subject-Completed Forms
Screening/Dispensing Visit	

• Informed Consent

• Initial Lens Performance Rating Scales (Habitual Lenses)

• Baseline Questionnaire

• Abbreviated Lens Performance Rating Scales (Study lenses)

Visit Name	Subject-Completed Forms
1-Week Follow-up Visit	
 
• Lens Performance Rating Scales (Study Lenses)
 

At least 7 days after the 1-Week Follow-Up Visit but before the 3-Week Follow-Up Visit	
 
• Online Consumer Survey
 

3-Week Follow-up Visit	
 
• Lens Performance Rating Scales (Study Lenses)
 

**Note:** *If the subject returns for an Unscheduled Visit, Symptoms and Complaints should be assessed.*

### 5.1.1 Screening/Dispensing Visit

**Note:** *All VA measurements MUST be made using a phoropter.*

A Screening Log will be provided by the Sponsor to track all consented subjects who the Investigator interviews regarding the study. Once all available lines on the Screening Log have been completed, or the Investigator has fulfilled his/her quota of subjects, the Investigator will sign and date the form to verify that all the subjects who interviewed for the study have provided informed consent and HIPAA authorization.

After obtaining written informed consent, prospective subjects will be screened to determine whether they meet the entry criteria for the study.

Screening/Dispensing will proceed as follows:

- Enter the subject information on the next available line of the Screening Log:
  - Subject initials
  - Subject date of birth
  - Screening date
- Collect demographic and the following habitual contact lens use history information and record in the subject's source document:
  - Over the last week, Average number of days per week worn
  - Over the last week, Average daily wearing time, hours per day
  - Over the last week, Average hours of comfortable wear per day
  - Over the last week, Average number of times used rewetting drops per day
  - Hours lenses worn on the day of this visit
  - Current lens brand
  - Current lens care products
- Collect ocular medical history (within 1 year of signing the ICF) and concomitant medications. Concomitant medications (as defined for this study) include any medications for ocular conditions taken within 30 days of signing the ICF.
- Have the participant complete the Lens Performance Rating Scales for habitual lenses using the 0-100 rating scales provided by the Sponsor.
- Have the participant complete the Symptoms/Complaints Form for habitual lenses
- Perform the following baseline assessments (with habitual lenses) and record in the subject's source document:

- Distance, intermediate, and near lens VA (OU) with a high contrast logMAR visual acuity chart

g. Perform the following baseline assessments (without lenses) and record in the subject's source document:

- Spherocylindrical refraction
- Add power
- High-contrast distance BSCVA (OD, OS, and OU logMAR)
- High-contrast intermediate logMAR BSCVA (OU w/near add)
- High-contrast near logMAR BSCVA (OU w/near add)
- Keratometry

h. Pupil measurement

i. Perform a slit lamp examination. Record all slit lamp findings and at a minimum sketch the following in the subject's source document:

- Any ungraded finding marked as “PRESENT”
- Any corneal scars
- Any corneal staining
- Any corneal infiltrate
- Any other graded slit lamp findings Grade >2

j. Assess eligibility. Indicate on the Screening Log whether the subject is a “Screen Pass” or “Screen Fail.” “Screen Fail” subjects are ineligible and cannot be enrolled in the study. The reason for screen failure must be documented on the Screening Log and in the subject record and maintained with a copy of their ICF.

k. Administer the Baseline Questionnaire.

l. Dispense 10 study contact lenses per eye according to the Fitting Guide and dispense all study materials.

- **The subject MUST insert the study lenses at this visit.**

*Note: Study lenses should be allowed to equilibrate a minimum of 10 minutes on the eye. Subjects should be encouraged to walk around, read, and/or look outside while the lens is equilibrating. If the vision is unsatisfactory, the lenses should be refined by adding add power according to the fitting guide to achieve acceptable vision. Number of refinements completed to achieve satisfactory vision in each eye will need to be collected.*

- Order remaining study contact lenses on Stock Material Order Form.

m. For the dispensed lenses, perform the following assessments:

- Dispensed lens sphere power
- Dispensed lens add power (high, low, or none)
- Distance (OU), intermediate (OU), and near (OU) lens VA
- Lens wettability
- Lens centration
- Lens movement

n. Compare the high-contrast OU distance lens VA to the high-contrast OU distance BSCVA obtained at this visit. If the VA has decreased by  $\geq 10$  letters, explain.

- o. Have the subject complete the abbreviated Lens Performance Rating Scales for study lenses using the 0-100 rating scales provided by the Sponsor.
- p. Collect/assess all AEs/ADEs, including serious or significant non-serious AEs.
- q. Provide instructions for study contact lens wear to the subject and instruct the subject to wear their study lenses to the 1-Week Follow-Up Visit.
- r. Register subject information in ePRO system **while subject is in office**. This should be done only for eligible, dispensed subjects. Subject data to be entered for registration:
  - Subject number
  - Date of birth
  - Subject phone number (text capability)
  - Screen date
- s. After registration, the subject will log into the ePRO Portal with their User ID and Temporary Password. After initial login, they will be prompted to update their password, create a security question, confirm consent, and complete a quick training session of the use of the ePRO system. Once all these steps are done at the screening visit, the subject is considered “active” in the ePRO system.
- t. Provide subject with Online Consumer Survey Instructions.
- u. Complete the Screening/Dispensing Visit eCRFs. If the subject is discontinued or exited at this visit, complete Exit Visit eCRFs.

### 5.1.2 1-Week Follow-up Visit

***Note: If the subject does not come to a visit wearing study lenses and is not experiencing any problems, it is preferred if the current visit is rescheduled within the visit window.***

***Note: All VA measurements MUST be made using a phoropter.***

- a. Collect changes in ocular medical history and concomitant medications
- b. Collect the following study lens information from the subject:
  - Over the last week, Average number of days per week worn
  - Over the last week, Average daily wearing time, hours per day
  - Over the last week, Average hours of comfortable wear per day
  - Hours lenses worn on the day of this visit
  - Over the last week, average number of times used rewetting drops per day. (Note: Only to be completed by subjects reporting rewetting drop use with habitual lenses at the Dispensing Visit.)
- c. Collect the Lens Performance Ratings for dispensed contact lenses using the 0-100 rating scales provided by the Sponsor.
- d. Collect the Symptoms/Complaints for dispensed lenses.
- e. If the subject did not come to the visit wearing one or more study lenses, go to step g. Otherwise, evaluate the study lenses (while on eye) and record the following assessments:
  - Distance (OU), intermediate (OU), and near (OU) lens VA
  - Lens wettability
  - Lens deposits (type, percent, and degree)

- Lens centration
- Lens movement

Compare the high-contrast OU distance lens VA to the high-contrast OU distance BSCVA obtained at the Screening/Dispensing visit. If the VA has decreased by  $\geq 10$  letters, explain.

f. If the subject requires a change to their study lens power at the 1-Week Follow-Up Visit, collect the worn lenses from the subject, and the unworn lenses for the eye(s) requiring a change, adjust the lens power, dispense study lenses with the appropriate power according to the Fitting Guide, and perform assessment in step e, (with exception of deposits), after an equilibration time of 10 minutes.

***Note: Study lenses should be allowed to equilibrate a minimum of 10 minutes on the eye. Subjects should be encouraged to walk around, read, and/or look outside while the lens is equilibrating. If the first set of study lenses is unacceptable to the subject, adjust study lenses according to the Fitting Guide to achieve acceptable vision. Continue to adjust until vision is acceptable. Allow the study lens(es) to equilibrate a minimum of 10 minutes on the eye before conducting the assessments in step e. Number of refinements completed to achieve satisfactory vision in each eye will need to be collected.***

g. Perform a slit lamp examination (remove the lenses if the subject wore lenses to the visit). Record all slit lamp findings and at a minimum sketch the following in the subject's source document:

- Any ungraded finding marked as “PRESENT”
- Any corneal scars
- Any corneal staining
- Any corneal infiltrate
- Any other graded slit lamp findings Grade  $>2$

h. Collect/assess all AEs/ADEs, including serious or significant non-serious AEs.

i. Dispense 20 study contact lenses per eye according to the Fitting Guide.

j. Instruct the subject to wear their study lenses to the 3-Week Follow-Up Visit.

k. Remind the subject to complete Online Consumer Survey at least 7 days after this visit but before the 3-Week Follow-Up Visit.

l. Collect all worn study lenses from the subject.

***Note: The Investigator must return all worn study lenses to the Sponsor in the return materials provided. All study contact lenses must be accompanied by a Product Accountability Log.***

m. Confirm 1-week visit (V2) in the ePRO system (triggers text reminders for survey completion).

n. Complete the 1-Week Follow-Up Visit eCRF. If the subject is discontinued or exited at this visit, complete Exit Visit eCRFs.

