***Note: If the subject is experiencing problems, complete the entire Unscheduled Visit Form.***

- b) Collect the following information from the subject regarding study lenses:
  - Average number of days per week worn
  - Average daily wearing time, hours per day
  - Average hours of comfortable wear per day
  - Hours lenses worn on the day of this visit
  - Rewetting drop use.
- c) Collect Symptoms/Complaints.
- d) If the subject did not come to the visit wearing one or more study lenses, go to step e. Otherwise, evaluate the study lenses (while on eye), and record the following assessments:
  - Distance (OU), intermediate (OU), and near (OU) lens VA
  - Lens wettability
  - Lens deposits
  - Lens centration
  - Lens movementCompare the high contrast OU distance lens VA to the high contrast OU distance BSCVA obtained at the Screening/Dispensing Visit. If the VA has decreased by  $\geq 10$  letters or more, explain.
- e) Perform a slit lamp examination (remove the lenses if the subject wore lenses to the visit). Record all slit lamp findings and at a minimum sketch the following in the subject's source document:
  - Any ungraded finding marked as "PRESENT"
  - Any corneal scars
  - Any corneal staining
  - Any corneal infiltrate
  - Any other graded slit lamp findings Grade  $>2$
- f) If an unscheduled lens replenishment for the same lens is required, dispense additional lenses, and collect the following:
  - Primary reason for replacement

- Dispensed lens sphere power
- Dispensed lens add power (high, low)
- Distance (OU), intermediate (OU), and near (OU) lens VA
- Lens wettability
- Lens centration
- Lens movement

**Note:** *Remember to record replenishment on the Product Accountability Log.*

**Note:** *The Investigator must return all worn and unworn study lenses to the Sponsor in the return materials provided. All study contact lenses must be accompanied by a Product Accountability Log.*

- If an unscheduled lens replacement requires a change in lens power for unacceptable vision, follow steps f, g, h, and i in [Section 5.1.2](#).
- The Unscheduled Visit eCRFs should be completed.

If the subject is discontinued or exited at this visit, complete the Exit Visit eCRFs.

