## 7. Follow-up Care

- From the day of dispensing, the following schedule is required for this study.
  - 1-Week Follow-Up Visit
  - 3-Week Follow-Up Visit

- Prior to a follow-up examination, the contact lenses should be worn for approximately 1 continuous hour and the subject should be asked to identify any problems which might be occurring related to contact lens wear.
- With lenses in place on the eyes, evaluate fitting performance to assure that CRITERIA OF A WELL FITTED LENS continue to be satisfied. Examine the lenses closely for surface deposition and/or damage.
- After the lens removal, instill sodium fluorescein (unless contraindicated) into the eyes and conduct a thorough biomicroscopy examination.
  - o The presence of vertical corneal striae in the posterior central cornea and/or corneal neovascularization may be indicative of excessive corneal edema.
  - o The presence of corneal staining and/or limbal-conjunctival hyperemia can be indicative of an unclean lens, a reaction to solution preservatives, excessive lens wear, and/or a poorly fitting lens.
  - o Papillary conjunctival changes may be indicative of an unclean and/or damaged lens. If any of the above observations are judged abnormal, various professional judgments are necessary to alleviate the problem and restore the eye to optimal conditions.

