6.5.12.3 Slit Lamp Examination

Slit lamp examination (without lenses) will be performed at the Screening/Dispensing Visit and at all follow-up visits.

Epithelial Edema, Epithelial Microcysts, Stromal Edema, Endothelial regularity, Corneal Staining, Limbal Injection, Bulbar Injection, Upper Lid Tarsal Conjunctival Abnormalities, Corneal Neovascularization, and Corneal Infiltrates will be assessment on the following scale:

- Grade 0 = None
- Grade 1 = Trace
- Grade 2 = Mild
- Grade 3 = Moderate
- Grade 4 = Severe

Bulbar Conjunctival Lens Compression/Indentation, New Corneal Scar, and Other Slit-Lamp Findings will be assessed as follows:

- Present
- Absent

All slit lamp measures will be assessed for each eye and will be summarized categorically by visit and visit type (unscheduled/scheduled). Eyes/subjects with multiple visits in a visit category will be counted once for the worst case. The Total column will summarize the worst case (from scheduled and unscheduled visits) for each visit category. In addition, a summary of assessment over all follow-up visits will be provided using the worst case.

A listing of eyes with corneal infiltrates and details of the of corneal infiltrate evaluation will be presented.

A listing of eyes with corneal scars and details of follow-up assessments will be presented.

A subject listing of all slit lamp findings data will also be presented.

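### As lettered, the only 1-Week slit-lamp exam of a refitted eye comes after the refit, so grades of short-lived signs may mix the week's wear with refit handling

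*Protocol*

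**What the plan says.** Protocol Section 5.1.2 sets out the 1-Week Visit in lettered steps. Step e assesses the worn lenses on the eye, and sends a subject who arrives without lenses forward to step g. Step f applies only to subjects who need a power change. The site is to "collect the worn lenses from the subject, and the unworn lenses for the eye(s) requiring a change", then "adjust the lens power, dispense study lenses with the appropriate power according to the Fitting Guide, and perform assessment in step e", leaving out deposits and waiting 10 minutes for the new lenses to settle. If the first new pair is not acceptable, the note to step f adds: "Continue to adjust until vision is acceptable". Step g then reads: "Perform a slit lamp examination (remove the lenses if the subject wore lenses to the visit". Adverse events are assessed in step h, and the 20-lens supply is dispensed in step i.

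For Unscheduled Visits, Section 5.1.5 places a slit-lamp exam at step e, ahead of any replacement, and then says: "If an unscheduled lens replacement requires a change in lens power for unacceptable vision, follow steps f, g, h, and i in" Section 5.1.2. The Fitting Guide (Appendix D, Follow-up Care) says: "After the lens removal, instill sodium fluorescein (unless contraindicated) into the eyes and conduct a thorough biomicroscopy examination".

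SAP Section 6.5.12.3 summarises ten graded signs by visit and visit type. It adds three present/absent items: "Bulbar Conjunctival Lens Compression/Indentation, New Corneal Scar, and Other Slit-Lamp Findings will be assessed as follows". It also reports the worst case over all follow-up visits. It has no separate rule for eyes examined after a refit.

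**The concern.** The week-1 slit-lamp result should show how the eye looks after about a week in the study lens. For a refitted subject the lens last on the eye before step g is a fresh trial lens, not the one worn to the visit. The Fitting Guide treats staining and limbal or conjunctival redness as possible signs of overwear or poor fit. If such a sign is first graded after one or more lens changes, it cannot be assigned to the worn lens or to the refit. A sign that fades quickly, such as lens indentation, may also have lessened by then.

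The same exam feeds the adverse-event assessment in step h, where staining of Grade 3 or more counts as a significant event under Section 6.1.2. Refitted subjects are also not a random subset: they are the ones whose lens power had to be changed.

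**Working it through.** The plan gives no figure on this point, so the check is mainly one of order.

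**Order of exam and lens insertion, by visit**

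| Visit | Slit lamp | New lenses on the eye | Exam before insertion? |
|---|---|---|---|
| Day 1 (5.1.1) | step i | step l | yes |
| 1-Week, refitted (5.1.2) | step g | step f | no |
| 3-Week (5.1.3) | step f | no refit step | not applicable |
| Unscheduled, power change (5.1.5) | step e, then step g of 5.1.2 | step f of 5.1.2 | yes, and again afterwards |

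The scheduled 1-Week refit is the only row with lens insertion and no exam before it. The jump from step e to step g shows that the letters are meant as a route through the visit. Step g's removal note mentions only lenses worn to the visit. In a refit these have already been collected, so the note does not cover the new pair, although SAP 6.5.12.3 describes an exam without lenses.

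**Time on new lenses before the exam.** With k trial pairs at 10 minutes or more each, the time is at least 10k minutes: 10, 20 and 30 minutes for k = 1, 2 and 3. The protocol sets no limit on k.

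**Eyes affected.** The documents give no refit rate; SAP 6.5.10.5.3 says only that a change may be needed. Assume a share s of 5% to 30% of the 600 planned eyes: 0.05 × 600 = 30 and 0.30 × 600 = 180.

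**Effect on a pooled week-1 finding rate.** Let d be the change in the probability of a finding that the refit causes in refitted eyes. The pooled rate then shifts by s × d. Taking d from 2% to 20%, also an assumption:

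- s = 5%, d = 2%: 0.1 percentage points
- s = 10%, d = 5%: 0.5 points
- s = 30%, d = 20%: 6.0 points

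Handling would raise the rate and recovery after removal would lower it, so even the sign is uncertain.

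**Which signs.** This is clinical judgement; the documents hold no data on it. Staining, limbal or bulbar injection and lens indentation could plausibly change over one or more lens changes. Infiltrates, scars, neovascularization, microcysts and tarsal changes should not.

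**The case against.** The strongest reply is that the letters are not a strict timeline. Step l collects all worn lenses after dispensing, although step f has already collected them in a refit. Step g's removal note would suit a site that examines the eye as the worn lenses come off, and the Fitting Guide also places biomicroscopy after lens removal. Appendix B, which holds the clinical methods, is blacked out and might contain a timing rule. This stands as a reason to say *as lettered*. It does not settle the matter, because a site that follows the steps as written examines after the refit. The Fitting Guide does not help either way: it does not mention refits.

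A second reply is that fluorescein discolors lenses, which could be a reason to fit first. The protocol does not give that reason. The Fitting Guide provides for a flush and a wait before new lenses, and Day 1 already examines before insertion.

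Third, the claim that short-lived signs change has no source in the documents, and no size or direction is known. That stands, and it limits the point to what may happen.

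Two stronger readings are tempting. A reader might infer that the week-1 grades of refitted eyes no longer describe the week at all. The documents do not support this: those eyes did have the week of wear, and slow-changing findings should still show it. A reader might also infer that subjects go home with new lenses on an unexamined eye. They do not: steps g and h both come before the supply is dispensed in step i, and every subject is due a further exam at Week 3.

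**Conclusion.** The point holds in limited form. As lettered, a subject refitted at the 1-Week Visit has a single slit-lamp exam, after the worn lenses are off and at least one new pair has settled. The grades of short-lived signs in those eyes may combine a week of wear with the refit. SAP 6.5.12.3 leaves no way to separate the two, in the week-1 table or in the worst case over follow-up.

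The number of eyes is not stated, and the size of the effect is unknown. The range of 0.1 to 6.0 percentage points rests wholly on assumed refit shares and assumed effects. Slit-lamp results are descriptive, so no hypothesis test, primary endpoint or power figure depends on them. The change is still worth making, because it is cheap and the mix cannot be undone after data collection.

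**What to change.** **Protocol.** Reconcile Section 5.1.2 with Sections 5.1.1 and 5.1.5 and with the Fitting Guide's follow-up text, so that the 1-Week slit-lamp record is taken after worn-lens removal and before any trial lens is inserted. If steps f and g change places, two cross-references must change as well. The jump in step e would otherwise send subjects without lenses to the refit step. The list of steps in 5.1.5 would otherwise call for a second slit-lamp exam before the refit. The slit-lamp step should cover removal of any lens on the eye, not only lenses worn to the visit.

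**eCRF.** Add a field for whether the exam came before or after a refit.

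**SAP.** In 6.5.12.3, name the exam before insertion as the record that is summarised, at scheduled and unscheduled visits alike. This matters if a second exam is kept after a refit, because the worst-value rule in 6.5.2 would otherwise bring refit effects back in. Show week-1 results with and without any eyes examined after a refit.

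**Cost.** A reordering of two steps, two cross-references, one data field and one extra table. The real downside falls on refitted subjects. The Fitting Guide's flush and 5-minute wait after fluorescein, or 1 hour if flushing is not possible, would come before the new lenses go in, and so before their visual acuity and wettability are assessed.
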